9.3 Efficacy Analysis

Assessment of efficacy of VX-210 treatment is one of the primary objectives of this pivotal study. All efficacy endpoints will be analyzed based on the FAS. All Efficacy data will be presented in listings based on the All Subjects Set.

The primary efficacy analysis in this study targets an estimand that would assess efficacy by using the change from baseline in the UEMS score at 6 months after treatment, focusing on the effect attributable to the initially randomized treatment.

Such an estimand targets the effect of the initially randomized treatment regimen, with consideration for the fact that enrolled subjects will also receive standard of care. With such

an estimand, all subjects in FAS with their primary efficacy endpoint data collected at 6 weeks, 3 months, 6 months, and 12 months after treatment are used to assess the targeted treatment effect. The primary efficacy analysis will be based on a mixed-effects model for repeated measures (MMRM), estimated using restricted maximum likelihood, treating the change from baseline in the UEMS score at 6 weeks, 3 months, 6 months, and 12 months after treatment as the dependent variable. If change from baseline in the UEMS score is missing after the visit windows rules have been applied, the missing value will be assumed to be Missing At Random (MAR) conditional on the observed data. With use of the MMRM model and the MAR assumption, no missing data will be explicitly imputed.

[REDACTED]

The primary result obtained from the primary efficacy analysis will be the estimated mean treatment effect at 6 months after treatment, and the estimated mean treatment effects at 6 weeks, 3 months, and 12 months after treatment, obtained from the model established, will also be provided.

[REDACTED]

9.3.1 Analysis of Primary Efficacy Variable(s)

9.3.1.1 Definition of Variable

Upper Extremity Motor Score (UEMS)

UEMS is a subset of the ISNCSCI examination, an assessment developed by the American Spinal Injury Association (ASIA) that is widely used for evaluating efficacy in SCI clinical trials. The range of the UEMS score is 0-50. The score collected in the CRF will be directly used in the analysis.

9.3.1.2 Primary Analysis

The UEMS score will be summarized at baseline, 6 weeks, 3 months, 6 months, and 12 months after treatment using the descriptive summary statistics by treatment group. The change from baseline in the UEMS score at 6 weeks, 3 months, 6 months, and 12 months after treatment will also be summarized descriptively by treatment group.

The primary efficacy endpoint is the change from baseline in the UEMS score at 6 months after treatment. The null hypothesis to be tested is that the mean change from baseline in the UEMS score at 6 months after treatment is the same for 9 mg dose of VX-210 and placebo.

The primary efficacy analysis will be based on an MMRM model. The model will include the change from baseline in the UEMS score at 6 weeks, 3 months, 6 months, and 12 months after treatment as the dependent variable; treatment, visit, and treatment-by-visit interaction as fixed effects; and subject as a random effect, with adjustment for age and AIS grade (only including A versus B with sacral pinprick preservation versus B without sacral pinprick preservation) at baseline. In the MMRM model, visit will be treated as a class variable, and an unstructured covariance matrix will be assumed to model the within-subject variability. Denominator degrees of freedom for the F-test for fixed effects will be estimated using the

Kenward-Roger approximation. If change from baseline in the UEMS score is missing after the visit windows rules have been applied, the missing value will be assumed to be MAR conditional on the observed data. With an MMRM model based on restricted maximum likelihood estimation as the primary efficacy analysis and under the MAR assumption, no imputation of missing data will be performed.

The primary result obtained from the primary efficacy analysis will be the estimated mean treatment effect (Least Squares [LS] means difference) at 6 months after treatment. The estimated mean treatment effect at 6 months after treatment, a 95% confidence interval (CI), and a 2-sided *P* value will be provided. Furthermore, the estimated mean treatment effects (with 95% CI) at 6 weeks, 3 months, and 12 months after treatment, obtained from the model established, will also be provided.

If there is a convergence problem due to use of an unstructured covariance matrix, the unstructured covariance matrix will be replaced by a compound symmetric covariance matrix to model the within-subject variability.

All UEMS data will be presented in a subject listing.

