12.3.3.1 Analysis of Primary Efficacy Variables

The primary efficacy endpoint is the change from baseline in UEMS at 6 months after treatment. The null hypothesis to be tested is that the mean change from baseline in UEMS at 6 months after treatment is the same for 9-mg dose of VX-210 and placebo.

The primary analysis will be based on a mixed-effects model for repeated measures (MMRM). The model will include the change from baseline in UEMS as the dependent variable; treatment, visit, and treatment-by-visit interaction as fixed effects; and subject as a

random effect, with adjustment for age and AIS grade (A versus B with sacral pinprick preservation versus B without sacral pinprick preservation) at baseline. In the model, visit will be treated as a class variable, and an unstructured covariance matrix will be assumed to model the within-subject variability. This model imposes no assumptions on the correlation structure and is considered robust. Denominator degrees of freedom for the F-test for fixed effects will be estimated using the Kenward-Roger approximation.⁵² With a mixed-effects model based on restricted maximum likelihood estimation as the primary analysis and assuming that, conditional on fixed and random effects, data are missing at random, no imputation of missing data will be performed.

The primary result obtained from the model will be the estimated mean treatment effect at 6 months after treatment. The estimated mean treatment effect, a 95% CI, and a 2-sided *P* value will be provided. Furthermore, the treatment effect at each postbaseline visit, obtained from the model, will also be provided.

If there is a convergence problem due to the use of an unstructured covariance matrix, the unstructured covariance matrix will be replaced by a compound symmetric covariance matrix to model the within-subject errors.

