7.2 Sample Size and Power

The primary efficacy endpoint is the change from baseline in UEMS at 6 months after treatment.

The null hypothesis to be tested is that the mean change from baseline in UEMS at 6 months after treatment is the same for 9-mg dose of VX-210 and placebo. This null hypothesis will be tested at 2-sided significance level $\alpha = 0.05$.

The sample size was calculated using a projected standard deviation (SD) of 6.0, based on the variability of improvement in UEMS scores of cervical subjects in the historical Sygen database. Anticipated withdrawal of 10% of subjects before the first follow-up assessment was also included in the sample size calculation.

If 9-mg dose group improves in UEMS by 4 points over placebo (a clinically meaningful increase), a total of approximately 100 subjects (approximately 50 per arm) will have approximately 82.1% power to detect a statistically significant treatment effect for 9-mg dose group compared to placebo, considering the interim futility analysis.

Based on the review of data from Anderson et al., the SD was projected to be 3.8 for SCIM III Self-Care subscore. [Table 7-1](#) presents the estimated power for detecting various

treatment differences between an active treatment group and the placebo group in SCIM III Self-Care subscore, assuming 45 randomized subjects with follow-up assessment in each treatment group without considering the possible power loss from the interim futility analysis.

Table 7-1 Power Estimates Under a Variety of Treatment Differences, Given 45 Randomized Subjects With Follow-up Assessments in Each Treatment Group

Mean Difference in SCIM III Self-Care Subscore	Power (%)
1	23
2	69
3	95

Power estimates are based on 2-sided t-test with $\alpha = 0.05$.

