7.3 Randomization

Subjects will be randomized to receive a single 9-mg dose of VX-210 in fibrin sealant, or a placebo (buffer solution) in fibrin sealant at a 1:1 ratio. Subjects will be stratified by age (<30 versus ≥ 30 years of age) and AIS grade (A versus B with sacral pinprick preservation versus B without sacral pinprick preservation) when they are randomized to the 2 study arms.

An interactive web or voice response system (IXRS) will be used to assign subjects to treatment. The randomization code will be produced by Vertex Biostatistics or a qualified randomization vendor. The Vertex study biostatistician will review and approve the dummy randomization list. The final randomization list will be generated and approved by an unblinded biostatistician or designee who is not a member of the study execution team.

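### The primary MMRM as written gives age and AIS grade one effect for all four visits; adding their visit interactions is a cheap gain in 6-month precision if AIS effects and variance grow after 6 weeks

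*SAP*

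**What the plan says.** SAP 9.3.1.2 models UEMS change at all four follow-up visits. Its mean model is "treatment, visit, and treatment-by-visit interaction as fixed effects; and subject as a random effect, with adjustment for age and AIS grade", with AIS in three levels. Visit is a class variable and the covariance is unstructured, with compound symmetry as the fallback. Protocol 12.3.3.1 uses the same construction ("random effect, with adjustment for age and AIS grade"), and so does the synopsis. None of the three lists a covariate-by-visit term.

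Under SAP 7.3, subjects are stratified by age (below 30 or not) and the three AIS categories "when they are randomized to the 2 study arms".

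SAP 7.2 gives the planning basis: "The sample size was calculated using a projected standard deviation (SD) of 6.0". No credit for covariate adjustment is mentioned. The result is "approximately 82.1% power to detect a statistically significant treatment effect for 9-mg dose group". Neither document gives an AIS effect by visit, an SD by visit or a between-visit correlation.

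**The concern.** The plan lets the treatment effect vary by visit and leaves the covariance free, yet it ties the effects of the two stratification factors to one value for a year. The outcome is a change from baseline, so at day 0 both the AIS difference and the variance are zero by construction, and both build up from there. If they are still building after 6 weeks, a common AIS coefficient cannot fit 6 months well.

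Under an unstructured covariance, that coefficient leans on the least variable visit. AIS variation missed at 6 months goes into the residual variance. Stratified randomization has already balanced AIS between arms, so this variation adds little to the true sampling error of the treatment difference, but the model SE still includes it. The cost would be a wider interval and some lost power on the primary endpoint.

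**Working it through.** **1. The plan's own figure.** Inputs from SAP 7.2 and 10.1: difference 4, SD 6.0, two-sided 0.05, 50 per arm less 10% = 45, futility look at about one third (15 per arm), boundary 1.19.

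- SE = 6 × √(2/45) = 1.265. Power without the look = Φ(4/1.265 − 1.96) = Φ(1.20) = 88.5%.
- With the look: P(interim difference ≥ 1.19 and final Z ≥ 1.96), correlation √(15/45) = 0.577, gives 82.65%. The plan states 82.1%, so it is reproduced to within 0.6 points.

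**2. Which visit drives a common coefficient.** With within-stratum covariance V over the four visits, the weights are V⁻¹1 / (1′V⁻¹1). All SDs and correlations below are assumptions.

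| SD at 6 wk, 3, 6, 12 mo | Correlation | Weights at 6 wk, 3, 6, 12 mo |
|---|---|---|
| 3.5, 4.8, 5.6, 6.2 | serial 0.85 | 1.30, −0.31, −0.05, 0.06 |
| same | exchangeable 0.8 | 1.32, 0.13, −0.16, −0.29 |
| same | exchangeable 0.6 | 0.90, 0.18, 0.00, −0.08 |
| 4.5, 5.1, 5.6, 5.8 | exchangeable 0.6 | 0.56, 0.27, 0.11, 0.06 |
| 5.6 throughout | serial 0.85 | 0.43, 0.07, 0.07, 0.43 |
| 5.6 throughout | exchangeable | 0.25 each |

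The 6-week visit dominates only when variance rises.

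**3. Large-sample SE excess at 6 months.** Assume an AIS mix of 65% A, 15% B with pinprick and 20% B without, the last with half the effect. Scoring these 0, 1 and 0.5, v = 0.15 + 0.20 × 0.25 − 0.25² = 0.1375. Let d be the true 6-month effect minus the pooled effect. Then excess = √(1 + v·d²/5.6²) − 1.

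| AIS effect by visit (B with pinprick minus A) | SD and correlation | Pooled | d | Excess |
|---|---|---|---|---|
| 1.6, 2.8, 4, 4.4 | rising, serial 0.85 | 1.29 | 2.71 | 1.6% |
| same | rising, exch. 0.8 | 0.55 | 3.45 | 2.6% |
| 2.4, 4.2, 6, 6.6 | rising, exch. 0.6 | 2.38 | 3.62 | 2.8% |
| 1, 3, 6, 7 | rising, serial 0.85 | 0.52 | 5.48 | 6.4% |
| same | rising, exch. 0.8 | −1.30 | 7.30 | 11.1% |
| 3.2, 5.6, 8, 8.8 | rising, exch. 0.8 | 1.10 | 6.90 | 10.0% |
| same | flat, exchangeable | 6.40 | 1.60 | 0.6% |

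"Rising" is the 3.5 to 6.2 pattern. With the milder rise (4.5 to 5.8), the 1, 3, 6, 7 pattern gives 3.3% (serial 0.85) and 6.4% (exchangeable 0.8). A different AIS mix moves the upper end by a point or two.

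**4. Simulation.** 90 subjects, blocks of 4 within the six strata, 1,500 runs per setting, t reference with 85 df in place of Kenward-Roger, final test only. The 6-week AIS effect is 40% of its 6-month size. Entries are the plan's model versus the model with covariate-by-visit terms.

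| 6-month AIS effect, SD pattern, correlation | Model SE / empirical SD (null) | Type I error | Power at 4 points |
|---|---|---|---|
| 4, rising, serial 0.85 | 1.02 vs 1.00 | 4.3% vs 4.7% | 90.3% vs 91.5% |
| 4, rising, exch. 0.8 | 1.03 vs 1.01 | 4.3% vs 4.7% | 90.6% vs 91.7% |
| 8, rising, serial 0.85 | 1.06 vs 1.00 | 3.6% vs 4.7% | 88.8% vs 91.5% |
| 8, rising, exch. 0.8 | 1.10 vs 1.01 | 3.3% vs 4.7% | 87.7% vs 91.7% |
| 8, rising, exch. 0.8, 15% drop-out | 1.10 vs 1.01 | 3.5% vs 4.9% | 87.0% vs 90.5% |
| 8, flat, exch. 0.6 | 1.03 vs 1.02 | 4.2% vs 4.5% | 92.7% vs 92.5% |

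The Monte Carlo SE is about 0.6 points for type I error and 0.8 for power; both models were fitted to the same data sets. The mean estimate for a true 4 was 4.00 to 4.06 in both models.

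**5. Against the planned power.** A 6-point AIS effect with within-stratum SD 5.6 gives total SD √(31.36 + 0.1375 × 36) = 6.03, close to the planned 6.0. Repeating step 1 with true SD 5.6 and an SE too large by 0, 2, 5 or 10% gives 86.7, 86.2, 85.5 or 84.2%, all above 82.65%. Only if 6.0 were itself the within-stratum SD would the figure drop, to 82.1, 81.1 or 79.3% for an excess of 2, 5 or 10%.

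**The case against.** The strongest reply is that the mechanism needs AIS effects and variance that both grow after 6 weeks, and the documents show neither. With flat variance, or under the compound-symmetric fallback with equal variances, no single visit dominates and the excess is negligible. A prespecified main-effects MMRM is unbiased here and errs conservatively. The interim MMRM was specified as similar to this model and has already been run, and changing the protocol text brings approvals and regulatory submission (protocol 13.2.3).

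Most of this stands. It limits the point to a conditional gain in efficiency, but gives no reason to keep the restriction. Zero change at day 0 makes some growth certain; only how much remains after 6 weeks is unknown. SAP section 4 still allows documented revisions before final lock and unblinding.

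A reader might infer more than the documents support:

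- *That the 6-month SE is certainly too large.* This depends on inputs the documents do not give.
- *That the 82.1% power is wrong.* It rests on SD 6.0 with no stated credit for adjustment, and step 5 shows room to spare when 6.0 is the total SD.
- *That the treatment estimate is biased or type I error inflated.* Neither occurred in the simulations.
- *That the loss could be much larger.* A 9-point AIS gap with within-stratum SD 5.6 implies total SD √(31.36 + 0.1375 × 81) = 6.5, against the planned 6.0. The 8-point settings, at √(31.36 + 0.1375 × 64) = 6.3, are already above it.

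**Conclusion.** This is a worthwhile, cheap improvement and not an error in a stated figure. The model as written has no covariate-by-visit terms. How much precision that costs rests on the assumed AIS mix, AIS effects, by-visit SDs and correlations. The excess is negligible to about 2% in the milder settings and about 3–12% in the demanding ones, where a 6-month AIS effect of 6 points or more meets a steep rise in variance. The power at stake is at most about 4 percentage points, and it is precision beyond what the sample-size calculation counted on.

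**What to change.** In SAP 9.3.1.2, list the fixed effects as treatment, visit, treatment-by-visit, age, AIS grade, age-by-visit and AIS grade-by-visit. Align protocol 12.3.3.1 (and the matching synopsis text), and keep everything else. Make the change before final database lock and unblinding; later it would be post hoc.

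Costs:

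- Nine more mean parameters: (1 for age + 2 for AIS) × 3 additional visits. If covariate effects are truly constant, mean SE in simulation went from 1.178 to 1.182, about 0.3%.
- A documented revision of the SAP and protocol, with the approvals and submission that protocol 13.2.3 requires.
- A final model that differs slightly from the interim MMRM already run, which the revision should state.

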9.1 Inclusion Criteria

Subjects who meet all of the following inclusion criteria will be eligible.

1. Subject (or a witness, or his or her legally appointed and authorized representative) will sign and date an informed consent form (ICF).
2. Willing and able to comply with scheduled visits, treatment plan, laboratory tests, contraceptive guidelines, and other study procedures.
3. Subjects are male or female between 14 and 75 years of age, inclusive.
4. Acute traumatic cervical SCI, motor level of C4, C5, C6, or C7 on each side:
 - Screening UEMS score must be ≤ 16 points on each side.
 - AIS A subjects with a C4 motor level on both sides must have at least 1 point of motor activity between C5 and T1 on at least 1 side.
 - AIS B subjects with a C4 motor level on both sides must have at least 1 point of motor activity between C5 and C7 on at least 1 side.
5. AIS grade A or AIS grade B.
6. Scheduled and planned to undergo a spinal decompression/stabilization surgery that commences within 72 hours after the initial injury.
7. Computed tomography (CT) scan or magnetic resonance imaging (MRI) is consistent with the subject's neurological deficit.

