9.2 Exclusion Criteria

Subjects who meet any of the following exclusion criteria will not be eligible.

1. Participation in any other clinical study for acute SCI without approval by the sponsor (Vertex).
2. Inability to undergo decompression/stabilization surgery that commences within 72 hours after injury.

3. One or more upper extremity muscle groups untestable during screening ISNCSCI examination.
4. Acute SCI from gunshot or penetrating/stab wound; non-traumatic SCI (e.g., transverse myelitis, acute disc herniation); brachial plexus injury; complete spinal cord transection; or multifocal SCI.
5. Females who are breastfeeding or have a positive serum pregnancy test.
6. Body mass index (BMI) of ≥ 40 kg/m² at screening.
7. History of an adverse reaction to a fibrin sealant or its human or bovine components.
8. Unconsciousness or other mental impairment that precludes reliable ISNCSCI examination.
9. Known immunodeficiency, including human immunodeficiency virus, or use of immunosuppressive or cancer chemotherapeutic drugs.
10. Any significant medical or psychiatric comorbidities (e.g., neurologic, cardiac, respiratory, hepatic, bleeding/coagulation disorder, renal, active malignancy) that would significantly increase the risk of study enrollment and/or significantly interfere with study outcomes or assessments, in the judgment of the investigator. (Note: Subjects with chronic medical conditions that are well controlled are eligible for the study: e.g., a subject with mild and well-controlled asthma or diabetes would be eligible, whereas a subject with severe congestive heart failure limiting activity or severe cardiopulmonary disorder limiting exercise would not be eligible.)
11. Subject, or close relative of the subject, is the investigator or a subinvestigator, research assistant, pharmacist, study coordinator, or other staff directly involved with the conduct of the study at that site.

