4 INTRODUCTION

This statistical analysis plan (SAP) is for the final analysis and interim analysis (IA) of study VX15-210-101 and is based on the

- approved clinical study protocol, 14 April 2017, Version 2.0
- approved eCRF, dated May 24 2018, Version 4.0

VX15-210-101 is a Phase 2b/3, double-blind, randomized, placebo-controlled multicenter study. This study will assess the efficacy and safety of VX-210 in subjects with acute traumatic cervical spinal cord injury.

This SAP (Methods) documents the interim and final efficacy and safety analysis and data presentation for VX15-210-101.

SAS® Version 9.4 Software (SAS Institute, Cary, North Carolina, USA) or higher will be used to generate all statistical outputs (tables, figures, listings and datasets).

The SAP (Methods) Version 1.0 was finalized and approved before the data cut for the interim analysis. The interim analysis methods specified in Section 10.1 of the SAP (Methods) Version 1.0 were implemented during the interim analysis. Any revisions to the approved SAP (Methods) Version 1.0 will be documented and approved prior to the final clinical database lock and treatment unblinding for the study.

Any changes made to the SAP (Methods) after the clinical data lock has occurred will be documented in the clinical study report for this study.

The analysis addressing the pharmacokinetic (PK) objective of the study will be described in the Clinical Pharmacology Analysis Plan (CPAP) which will be developed separately by the Clinical Pharmacology department at Vertex Pharmaceuticals Incorporated (Vertex). The independent data monitoring committee (IDMC) analyses are also described in a separate SAP.

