9.2.2 Demographics and Baseline Characteristics

Demographics and baseline characteristics will be summarized overall and by treatment group based on the Full Analysis Set.

Demographic data will include the following:

- Sex (female and male)
- Age at baseline (in years)
- Age group (<30 versus ≥30 years of age)
- Ethnicity (Hispanic or Latino, not Hispanic or Latino, and not collected per local regulations)
- Race (White, Black or African American, Asian, American Indian or Alaska Native, Native Hawaiian or Other Pacific Islander, not collected per local regulations, and Other)
- Country

Baseline characteristics will include the following:

- Weight (kg)
- Height (cm)
- BMI (kg/m²)
- AIS Grade (A or B with or B without sacral pinprick preservation)
- Baseline UEMS score (total, left and right)

All medical history will be coded using the latest version of Medical Dictionary for Regulatory Activities (MedDRA). Medical history will be summarized using descriptive statistics by MedDRA system organ class (SOC) and preferred term (PT). Medical history will also be displayed in a subject listing.

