10 SUMMARY OF INTERIM AND IDMC ANALYSES

10.1 Interim Analysis

An interim analysis will be conducted when approximately 33% of enrolled subjects have completed the 6-month follow-up visit. Based on the results of this interim analysis, the study may continue or stop for futility. The IDMC will conduct review of this interim analysis and make recommendation to the sponsor. If the study is considered unsuccessful at the time of the interim analysis, the study is to be terminated, study enrollment is to be stopped, and subjects are to be followed for safety reasons only.

Based on the review of the data provided at the interim analysis meeting, the IDMC will make a recommendation regarding whether the study should continue or should stop for futility. The guideline for futility stopping will be that the 9-mg dose group improves in UEMS by less than approximately 1.19 points over placebo for the approximately 33% of subjects analyzed, under the assumed standard deviation (SD) of 6.

The IDMC will review the observed SD at the time of the interim analysis. If the SD deviates from the assumption, the futility guide is adjusted to be that the study will be stopped for futility if conditional power (under observed primary endpoint treatment effect size) is <10.6% or the observed primary endpoint treatment effect size is <1.19. The following table presents examples of the futility boundary with respect to different sizes of SD. The last column refers to the minimum observed primary endpoint effect size that is required to achieve statistical significance under the given size of SD at the final analysis.

Table 10-1 Guidelines for Futility Stopping

Standard Deviation	Futility Boundary	Conditional Power (Under	Minimum Required Observed
---------------------------	--------------------------	---------------------------------	----------------------------------

		Observed Effect Size)	Effect Size at Final Analysis
4	1.19	25.1%	1.7
6	1.19	10.6%	2.5
8	1.59	10.6%	3.3
10	1.98	10.6%	4.1

In all analyses supporting this interim analysis, only the first 43 randomized subjects will be used unless otherwise specified; this sub-population includes approximately 33% of enrolled subjects who are dosed with placebo or 9-mg of VX-210 and who will have completed the 6-month follow-up visit at the time of the interim analysis data cut.

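### The primary MMRM omits baseline UEMS, which every eligible subject has; the analysis is valid, but a modest gain in precision at the final analysis is left unused

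*SAP*

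**What the plan says.** Protocol 12.3.3.1 and SAP 9.3.1.2 specify the same primary model for change in UEMS: treatment, visit and treatment-by-visit, with "subject as a random effect, with adjustment for age and AIS grade" (protocol: "random effect, with adjustment for age and AIS grade"), unstructured covariance and Kenward-Roger degrees of freedom. Baseline UEMS enters only by being subtracted. The visible text gives no reason for leaving it out as a covariate.

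The score should be complete. Protocol 9.1 requires "Screening UEMS score must be ≤ 16 points on each side", and protocol 9.2 excludes subjects with "One or more upper extremity muscle groups untestable during screening ISNCSCI examination". SAP 9.2.2 already summarises "Baseline UEMS score (total, left and right"). Randomisation is stratified by age group and AIS grade, not by UEMS.

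The planning SD of 6.0 is "based on the variability of improvement in UEMS scores of cervical subjects in the historical Sygen database" (SAP 7.2). SAP 10.1.2 has the interim use a model similar to the primary one, and SAP section 4 records that the interim methods have been implemented.

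**The concern.** Using a change score fixes the coefficient of baseline at 1. It does not remove any remaining dependence of recovery on the starting score within age and AIS grade; that stays in the error term. Eligible starting totals run from 1 point (for subjects at C4 on both sides) to 32 of 50 (16 per side), so there is room for such dependence.

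Two things are at stake. The 6-month confidence interval may be wider than the collected data require. And a chance imbalance in baseline UEMS goes uncorrected: with 45 per arm and SD 6, an imbalance of one standard error shifts the unadjusted estimate by about r × 1.265 points, or 0.38 points at r = 0.3. Neither affects validity under randomisation.

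**Working it through.** **Inputs from the documents.** Difference 4, SD 6.0, two-sided alpha 0.05, 50 per arm less 10% withdrawal = 45 per arm (SAP 7.2); futility boundary 1.19 at about one third of subjects, so 15 of 45 per arm (SAP 10.1).

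**Assumed, because the documents give no value.** r = partial correlation of baseline UEMS with 6-month change given age and AIS grade, 0 to 0.5. f = share of the SD-6.0 variance that age and AIS grade already explain, 0 to 30%.

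**Step 1: reproduce Table 10-1.** Conditional power under the observed effect is Φ((z/√t − 1.96)/√(1 − t)), with z = boundary/(SD·√(2/15)) and t = 1/3. At SD 6, z = 1.19/2.191 = 0.543, and Φ((0.941 − 1.96)/0.816) = 10.6%. All four rows give 25.1, 10.6, 10.6 and 10.6%, as printed. The last column, the "minimum observed primary endpoint effect size that is required to achieve statistical significance under the given size of SD", is 1.96·SD·√(2/45) = 1.65, 2.48, 3.31 and 4.13, against 1.7, 2.5, 3.3 and 4.1. So the plan's figures use 15 and 45 per arm and credit no covariate.

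**Step 2: power by formula, interim as run, only the final model adjusted.**
- Interim residual SD = 6√(1 − f), final residual SD = 6√((1 − f)(1 − r²)).
- SE = residual SD × √(2/15) at interim and × √(2/45) at final; covariance of the two estimates = 2 × (final residual variance)/45.
- Power is the bivariate normal probability that the interim estimate is at least 1.19 and the final estimate exceeds 1.987 × SE (t, 88 df). CI half-width = 1.987 × SE.

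| f | r | Power | Gain (points) | CI half-width |
|---|---|---|---|---|
| 0 | 0 | 82.2% | – | 2.51 |
| 0 | 0.2 | 83.1% | 0.9 | 2.46 |
| 0 | 0.3 | 84.2% | 1.9 | 2.40 |
| 0 | 0.5 | 87.1% | 4.9 | 2.18 |
| 20% | 0 | 88.6% | – | 2.25 |
| 20% | 0.2 | 89.1% | 0.56 | 2.20 |
| 20% | 0.3 | 89.8% | 1.21 | 2.14 |
| 20% | 0.5 | 91.4% | 2.8 | 1.95 |

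The first row reproduces the stated 82.1%. At f = 30% the gain is 0.39 points at r = 0.2 and 0.81 at r = 0.3. The formula ignores the cost of estimating the slopes.

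**Step 3: four-visit MMRM simulation, which includes that cost.** 10,000 trials per setting, the same data for both models; REML, unstructured covariance, complete data, residual df (85 or 84) in place of Kenward-Roger; futility look under the current model. Assumed: AIS split 70/15/15%, AR(1) correlation 0.8, visit SDs 3, 4.5, 6, 6.5 for f = 0 and 6 throughout for f = 20%, baseline slopes proportional to visit SD.

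| f | r | Current model | With baseline UEMS by visit | Change in 6-month variance |
|---|---|---|---|---|
| 0 | 0 | 81.4% | 81.1% | +1.2% |
| 0 | 0.1 | 81.3% | 81.3% | +0.1% |
| 0 | 0.2 | 81.1% | 81.9% | −2.9% |
| 0 | 0.3 | 81.1% | 82.9% | −8.0% |
| 0 | 0.5 | 81.3% | 86.2% | −24.1% |
| 20% | 0 | 87.0% | 86.8% | not tabulated |
| 20% | 0.2 | 87.1% | 87.4% | not tabulated |
| 20% | 0.3 | 87.0% | 88.1% | not tabulated |

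The Monte Carlo error of a paired power difference is about 0.2 points. Break-even is where 1.012 × (1 − r²) = 1, so r ≈ 0.11. With slopes that grow over visits (f = 0), a single common slope cuts the variance by only 6.0% at r = 0.3 and 17.0% at r = 0.5. Type I error of the final test at r = 0.3 is 5.2% under both models.

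**The case against.** The strongest case is that nothing is wrong: protocol and SAP agree, the model is valid, and the power claim holds. The benefit rests on an r that no document supplies, and only what remains after the change score, age and AIS grade counts. At r = 0.2 to 0.3 the half-width shrinks by 0.05 to 0.11 points, against a 4-point target. The 82% also includes the risk of stopping at an interim that has since been run: the chance of passing it at the planned effect is 90.0%, so power given continuation is 82.24/90.02 = 91.4%, rising only to 93.5% at r = 0.3. Changing the primary model of a study described as pivotal, after the IDMC has seen unblinded efficacy data, has a cost in credibility; a supportive analysis would avoid it. Finally, redactions in SAP 9.3 and gaps in section numbering (SAP 9.3.2.1 to 9.3.4, protocol 12.3.3.2 to 12.3.3.4) may hide such an analysis.

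Most of this stands as a limit on size. The gain is uncertain and probably modest. The advantage of by-visit slopes over a common slope depends on slopes growing over time, and the f = 0 and f = 20% simulations also differ in visit SDs, so the difference between them cannot be put down to f alone. None of it gives a reason for omitting the covariate, and the primary-model text is not redacted. A supportive analysis would show the narrower interval, but the primary test would not benefit. SAP section 4 allows the change: "Any revisions to the approved SAP (Methods) Version 1.0 will be documented and approved prior to the final clinical database lock" and treatment unblinding.

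**Conclusion.** The concern holds as a matter of precision only. The primary comparison is valid and the planned power is correct as stated. Relative to the current model, adding baseline UEMS by visit at the final analysis is worth, in the simulation at f = 0, about 0.8 power points at r = 0.2, 1.8 at 0.3 and 4.9 at 0.5. At f = 20% it is worth 0.3 points at r = 0.2 and 1.1 at 0.3. It costs a few tenths of a point if r is 0. The trade therefore favours adjustment unless r is below about 0.11. This rests on assumed r and f, the assumed visit pattern, complete data and 45 per arm at the final analysis. The point concerns the visible primary model; a supportive analysis with baseline UEMS may exist in redacted text.

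**What to change.** Before final database lock and unblinding, staff blinded to both treatment and interim results should revise SAP 9.3.1.2 so that the final MMRM includes the continuous baseline UEMS total and its interaction with visit. Keep the current model as a prespecified sensitivity analysis. Record the departure from protocol 12.3.3.1, with its date and the blinding status of those who made it. The completed interim need not be revisited.

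The cost is four fixed-effect parameters (one baseline slope per visit) and no new data. If r is 0, about 0.1 to 0.4 power points are lost. The revision is a documented change of the primary model after an IDMC-reviewed interim, and the last column of Table 10-1 would then describe the sensitivity model rather than the primary one.
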